#### **Hematologic toxicity**

- Grade 4 thrombocytopenia ( $<25 \times 10^9/L$ ) lasting  $>72$  hours or a platelet count  $\leq 10 \times 10^9/L$  at any time

- $\geq$  Grade 3 thrombocytopenia with bleeding (except epistaxis or gingival bleeding that is less than 24 hours in duration and does not require medical intervention, or normal menses) or requiring platelet transfusions
- Grade 4 anemia, unexplained by underlying disease
- Grade 4 neutropenia lasting  $>72$  hours
- Grade 3 febrile neutropenia lasting  $>72$  hours
- Grade 4 febrile neutropenia

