## 6.3 Treatments Administered (All Phases)

### 6.3.1 Dosing Instructions

#### *General*

Premedication with an antihistamine and acetaminophen is required for all subjects prior to infusion of TTI-621.

TTI-621 will be thawed at room temperature and the required dose diluted into 250 mL of 0.9% sodium chloride for injection USP as further described in the Pharmacy Manual. If not used immediately, the prepared infusate may be stored as described in the Pharmacy Manual. The assigned dose of TTI-621 will be administered IV over 60 minutes (see [Section 6.4.1](#) for expansion phase instructions). The start of the infusion (Time 0) is defined as after priming, immediately before commencement of the infusion. End of infusion is defined as the time immediately after the flush.

Vital signs will be monitored as outlined in [Section 7](#).

The individual dose is determined based on the subject's current body weight. Body weight can be rounded per institutional procedures when calculating doses. Body weight will be taken weekly through Week 8, then every other week (Weeks 10, 12, etc.) After Week 8, the weight taken at the prior visit may be used to calculate dose (e.g. weight at Week 8 used for Week 9 dosing).

Each subject will receive TTI-621 in accordance with the assigned dose until disease progression, unacceptable toxicity, or other reasons for treatment discontinuation occur. For patients who have been given weekly infusion of TTI-621 for more than a year and are receiving clinical benefit (objective response or clinically meaningful long-term stable disease), investigators may exercise their discretion to reduce the dosing frequency from weekly to bi-weekly following the discussion and approval from the sponsor or designees. In the context of treatment discontinuation, unacceptable toxicity will include any Grade 4 TTI-621-related nonhematologic toxicity or a TTI-621-related toxicity that requires a dose delay of more than 3 weeks.

In the absence of disease progression, subsequent TTI-621 doses may be delivered based upon subject's clinical status with dose modifications per [Section 6.5](#).

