Patients who experience a DLT (during DLT evaluation period) or a DLT-like toxicity within the first 21 days of treatment, generally, require that treatment with TTI-621 be permanently discontinued. The patient will be followed until resolution or stabilization of the event. The investigator and medical monitor will decide on a case-by-case basis if it is in the patients' best interest to continue the study treatment. If continuation of

treatment is in the patients' best interest, the dose of TTI-621 will be reduced by at least 1 dose level upon resumption of treatment following recovery of the toxicity or toxicities to a level that satisfies the retreatment criteria (see [Section 6.5.2](#)). The discussion and decision will be documented.

In managing toxicities, dose modification guidelines should be followed closely. However, based on the evolving safety data of TTI-621 and/or individual patient cases, alternative dose modifications may be recommended after discussion between the investigator and medical monitor to maximize exposure of study treatment while protecting patient safety. In principle, dose modification is only required per guidance as described below when the AE is determined to be related to the study drug. However, when non-study-drug related AEs, in the investigator's assessment, would likely result in a medical condition where continuous dosing would add unwanted physical burden and stress to the patient, temporarily withholding the study drug is allowed. Discussions between the investigator and medical monitor are highly encouraged in these instances.

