**Table 6-1: Dose Modifications for Dose 2 and Subsequent Doses**

Clinical Scenario	Action
Grade 3 thrombocytopenia or Grade 4 thrombocytopenia lasting $\leq$ 72 hours*	Continue TTI-621 at the same dose when the re-treatment criterion ( $\geq 75 \times 10^9/L$ or baseline) is met; no dose intensification until no occurrence of the same event at the re-challenge of the same dose (Part 3).
Grade 4 thrombocytopenia (platelet $<25 \times 10^9/L$ ) lasting $>72$ hours* or a platelet count $\leq 10 \times 10^9/L$ at any time	Delay TTI-621 dosing until the re-treatment criterion ( $\geq 75 \times 10^9/L$ or baseline) is met; transfuse platelet prophylactically against bleeding when platelet $<10K$ per ASCO practice guideline; Then resume TTI-621: 
 
• at the same dose if dose delay for 1 week;
 
• at a reduced dose by 1 dose level if dose delay for <math>> 1</math> week;
 
• at a reduced dose by 1 dose level if the event recurs
 
 Dose intensification can occur only when there is no occurrence of the same event upon re-dosing of TTI-621 at the same dose for two consecutive weeks. When dose reduction occurs, no further dose intensification will be allowed (Part 3).
$\geq$ Grade 3 thrombocytopenia (platelet $<50 \times 10^9/L$ ) with clinical bleeding (more than easily controlled epistaxis, mild gum bleeding or menses)	Delay TTI-621 dosing until the re-treatment criterion ( $\geq 75 \times 10^9/L$ or baseline) is met, and then resume TTI-621 at a reduced dose by 1 dose level. No further dose intensification (Part 3) will be allowed.
Grade 4 neutropenia (ANC $<500/\text{mm}^3$ ) lasting $>72$ hours* (unexplained by underlying disease)	Delay TTI-621 dosing when the re-treatment criterion (ANC $>1000/\text{mm}^3$ ) is met then resume TTI-621: 
 
• at the same dose if dose delay for 1 week
 
• at a reduced dose by 1 dose level if dose delay for <math>>1</math> week;
 
• at a reduced dose by 1 dose level if the event recurs
 
 Dose intensification (Part 3) can occur only when there is no occurrence of the same event upon re-dosing of TTI-621 at the same dose for two consecutive weeks. When dose reduction occurs, no further dose intensification will be allowed.

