Grade 3 febrile neutropenia lasting $>72$ hours*; or Grade 3 neutropenia with any clinical evidence of infection; or Grade 4 febrile neutropenia	Delay TTI-621 dosing until the re-treatment criterion (ANC $>1000/\text{mm}^3$ ) is met, then resume TTI-621 at a reduced dose by 1 dose level. When dose reduction occurs, no further dose intensification will be allowed (Part 3).

Grade 3 infusion reaction (infusion reactions lasting up to 24 hours including fevers, rigors, headaches, hypotension, dyspnea, and urticaria related to TTI-621)	
The current infusion should be stopped promptly and standard care management administered. The medical monitor should be informed about the occurrence of the Gr3 event and one of the following options will be discussed following case-by-case assessment between the investigator and the medical monitor:
 
 
• Restarting the infusion after medical intervention and after the patient's condition has stabilized with additional supportive care medications,
 
• Terminating the current infusion, but re-challenging at the next weekly dose. At the re-challenge, the patient should receive premedication with corticosteroid per standard institution practice and/or established guidelines (Roselló et al., 2017); a slower rate of infusion and/or a lower dose of TTI-621 should be considered.
 
• Permanently discontinuing the study treatment. Do not intensify dose (Part 3)
 

Grade 4 infusion reaction (anaphylaxis or other life-threatening reactions lasting more than 24 hours)	Permanently discontinue TTI-621

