
Grade 3 or greater non-hematologic toxicity related to TTI-621 with the following exceptions:
 
 
• Grade 3 nausea and/or vomiting lasting <72 hours with standard supportive care
 
• Transient Grade 3 fatigue lasting <math>\leq</math>72 hours
 
• Transient asymptomatic Grade 3 laboratory abnormalities that last <72 hours with standard supportive care and considered not clinically significant following agreement between investigators and the sponsor or designees.
 
	
For Grade 3 events, delay TTI-621 dosing until the re-treatment criteria is met, then resume TTI-621 at a reduced dose by 1 dose level.
 
No dose reduction is required for the exceptions listed.
 
For Grade 4 events, discontinuation of TTI-621 should be considered. If, per investigator's assessment, it is in the patient's best interest to continue the treatment, TTI-621 treatment can be resumed when the AE resolves to a level that meets the re-treatment criteria
 
Do not intensify dose (Part 3)

Grade 3 or greater non-hematologic toxicity NOT related to TTI-621	Investigator's discretion to withhold or decrease dose of TTI-621. Do not intensify dose of TTI-621 until the resolution of the AEs to Grade 1, baseline, or a level (must be $\leq$ Grade 2) determined to be acceptable per investigator assessment (Part 3)

Grade 3 anemia	
Delay TTI-621 dosing until resolution to <math>\leq</math> Grade 1 or baseline, then resume TTI-621 treatment:
 
 
• at the same dose if dose delay for 1 week;
 
• at a reduced dose by 1 dose level if dose delay for <math>> 1</math> week;
 
• at a reduced dose by 1 dose level if the event recurs
 
• Dose intensification can occur only when there is no occurrence of the same event upon re-dosing of TTI-621 at the same dose for two consecutive weeks. When dose reduction occurs, no further dose intensification will be allowed (Part 3).
 

Grade 4 anemia	
Discontinuation of TTI-622 should be considered. If it is in the patient's best interest to continue TTI-622 per investigator assessment, withhold dose until resolved to <math>\leq</math> Grade 1 or baseline, then reduce by 1 dose level.

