## 6.7 Management of Clinical Events

### *Infusion-Related Reactions (IRR)*

Premedication with an antihistamine and acetaminophen is required for all subjects prior to infusion of TTI-621. During and immediately after infusion, patients will be closely monitored for signs and symptoms of allergic reactions. In the event of a reaction of any severity during the infusion itself, the infusion should be stopped and standard institutional supportive care administered.

Grade 1 or 2: If the reaction was Grade 1 or 2 in severity and the signs and symptoms have fully resolved, the infusion may be restarted. Any patient who experiences a Grade 2 allergic reaction must receive premedication with corticosteroids per standard institutional supportive care prior to receiving subsequent infusions.

Grade 3: If a patient experiences a Grade 3 IRR, the investigator may consider the following: 1) restarting the infusion after medical intervention and after the patient's condition has stabilized with additional supportive care medications, 2) terminating the current infusion, but re-challenging at the next weekly dose, or 3) permanently discontinuing the study treatment. When re-challenge occurs, the patient should receive pre-medication with corticosteroid per standard institutional practice, and a slower infusion rate and/or a reduced dose of TTI-621 should be considered. The investigator and medical monitor will decide to continue treating patients who experienced a Grade 3 IRR on a case-by-case basis. As with all AEs of special interest, the medical monitor should be apprised of any Grade 3 or higher infusion reaction that occurs during the study.

Grade 4: If the allergic reaction was Grade 4, the patient will be permanently discontinued from treatment.

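### Table 6-1 allows same-dose resumption after two events that are themselves Part 4 DLTs, and Section 6.6 does not exclude toxicity-reduced patients from later escalation; both conflict with Section 6.5.1

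*Protocol*

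**What the plan says.** Section 6.5 states that it governs Parts 2, 3 and 4 unless otherwise noted. Within it, and in Section 6.6, three sets of rules bear on what happens after a DLT.

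- **Section 6.5.1.** A DLT in the evaluation period, or a DLT-like toxicity in the first 21 days, generally ends treatment. If the investigator and medical monitor decide to continue, "the dose of TTI-621 will be reduced by at least 1 dose level upon resumption of treatment". The same section bars re-escalation after any reduction required by toxicity.
- **Section 6.6 (Part 4).** Treatment is held after a DLT in the first 21 days, the event counts toward the MTD, and the patient may go on at a reduced level. Once the MTD or recommended dose is known, all patients who have spent at least 4 weeks below it may move up. The conditions are no progression, no unacceptable treatment-related toxicity, recovery of adverse events, investigator discretion and medical monitor approval.
- **Table 6-1 (dose 2 onward).** For Grade 4 thrombocytopenia beyond 72 hours or platelets at or below 10 x 10^9/L, and for Grade 4 neutropenia beyond 72 hours, dosing resumes "at the same dose if dose delay for 1 week". It is reduced only if the delay is longer or the event recurs.

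Section 3.3.3 lists both of those events as DLTs when at least possibly related to treatment.

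**The concern.** Doses 2 and 3 fall inside the Part 4 DLT window and under Table 6-1. For the same event in the same week, a site therefore has two written instructions: stop or reduce (Sections 6.5.1 and 6.6), or resume unchanged after a one-week hold (Table 6-1). The table is what a site is likely to open when a count is low, and its two rows do not ask for a call to the medical monitor. Following it would give the patient again the dose that has just produced a DLT.

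The escalation clause has a similar gap. A patient reduced after a DLT at the level later recommended could be brought back to that level under Section 6.6, although Section 6.5.1 rules this out.

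The stake is the safety of individual patients, not the dose-finding inference.

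**Working it through.** The first two parts of the check set the rules side by side. Arithmetic enters only in judging how many patients could be involved.

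**1. Same event, two instructions**

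| Event in the DLT window | Section 3.3.3 | Sections 6.5.1 and 6.6 | Table 6-1, one-week delay |
|---|---|---|---|
| Grade 4 thrombocytopenia >72 h, or platelets ≤10 x 10^9/L | DLT | Stop, or resume at least 1 level lower | Same dose |
| Grade 4 neutropenia >72 h | DLT | Stop, or resume at least 1 level lower | Same dose |

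As an illustration, take a patient at Level 2 (0.7 mg/kg) who has Grade 4 thrombocytopenia for more than 72 hours after the Day 8 dose. The Day 15 dose is held, and platelets are back to at least 75 x 10^9/L by Day 22, so the delay is one week. Table 6-1 gives 0.7 mg/kg on Day 22. Sections 6.5.1 and 6.6 give no further drug, or the next lower level in Table 3-4, which is 0.5 mg/kg.

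**2. Re-escalation**

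- Section 3.3.2 allows the MTD to carry one DLT among at least six patients, so one patient may have had a DLT at the dose later recommended.
- If that patient continued at a lower level for 4 weeks, the dose condition in Section 6.6 is met.
- The remaining conditions do not clearly exclude the patient. Section 6.3.1 names two kinds of unacceptable toxicity: related Grade 4 non-hematologic events, and a related toxicity that delays dosing by more than 3 weeks. A platelet or neutrophil DLT that recovers sooner is neither.
- Section 6.5.1 bars the increase; Section 6.6 does not mention the bar. Section 6.5.2 repeats it only for toxicity that has not resolved by three weeks.

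**3. How many patients**

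The documents give no rate for either event in the first 21 days at 0.5 mg/kg or above. The nearest figure is in Section 1.8.4: Grade 4 post-dose platelets of any duration in 1 of 17 T-cell lymphoma patients at 0.5 mg/kg, reached by intensification from 0.2 mg/kg.

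- Point estimate: 1/17 = 0.0588, or 5.9%.
- Exact (Clopper-Pearson) 95% limits: the lower limit solves 1 − (1 − p)^17 = 0.025, so p = 1 − 0.975^(1/17) = 0.0015. The upper limit solves (1 − p)^17 + 17p(1 − p)^16 = 0.025, so p = 0.2869.
- Scaled to the roughly 25 patients planned for Part 4: 25 × 0.0588 = 1.5, with limits 25 × 0.0015 = 0.04 and 25 × 0.2869 = 7.2.

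This is a rough guide with errors in both directions. It counts short-lived events that are not DLTs, and Section 1.8.4 says the two Grade 4 thrombocytopenia DLTs at 0.3 mg/kg would not qualify under the revised criteria. On the other side, those 17 patients had already been exposed at lower doses. SAP Section 1.2.5 also describes a Part 4 dose of 2.0 mg/kg, four times 0.5 mg/kg, so 5.9% is not a ceiling.

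**The case against.** The best defence is that the specific rule governs. Section 6.5.1 first allows same-dose resumption in general and then carves out DLTs and early DLT-like events. Section 6.6 is headed for the DLT evaluation period. Section 6.5 applies unless otherwise noted, and Section 6.5.3 calls the table's content recommendations. Section 3.3.2 speaks of holding a dose under the guideline for events that are not DLTs. On that reading the table covers the same events only after the window, and nothing conflicts. In addition, continuing after a DLT needs a documented decision by the investigator and medical monitor. For re-escalation, the bar is categorical, Section 6.6 is permissive and needs the monitor's approval, and its natural target is patients assigned to lower cohorts.

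This is a plausible account of the intent, and it lowers the chance of a wrong dose. It does not remove the conflict. The DLT paragraph sits under general principles while the table row is specific to the event, so specificity can be argued either way. Section 6.5.3 repeats that dosing may restart at the same or a reduced level, with no exception for DLTs. No sentence sets precedence.

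A reader might go further and infer that five of the 11 rows contradict the post-DLT rule. The documents do not support that count; the other three rows are narrower ambiguities:

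- **Grade 3 or short Grade 4 thrombocytopenia.** The row says "Continue TTI-621 at the same dose when the re-treatment criterion" is met, while Section 3.3.3 makes such an event a DLT when it is "or requiring platelet transfusions". But the prophylactic transfusion threshold (below 10K in Table 6-1; the unit in Section 6.7 is evidently misprinted) falls in the next row. What remains is the non-bleeding patient transfused above that threshold on clinical judgment.
- **Grade 3 infusion reaction.** At re-challenge, "a slower rate of infusion and/or a lower dose of TTI-621 should be considered"; Section 6.7 likewise says "a slower infusion rate and/or a reduced dose of TTI-621 should be considered". The row requires case-by-case discussion with the medical monitor, and Section 6.5.1 permits alternative modifications after such discussion. It reads as a deliberate rule for this event.
- **Related Grade 4 non-hematologic toxicity.** After considering discontinuation, "TTI-621 treatment can be resumed when the AE resolves to a level that meets the re-treatment criteria". The row is silent on dose, and Section 6.5.1 fills that silence inside the window. The tension with Section 6.3.1, where "unacceptable toxicity will include any Grade 4 TTI-621-related nonhematologic toxicity", is a separate matter not tied to the window, and Section 6.9 says only that the patient may be withdrawn.

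**Conclusion.** The concern holds for two rows of Table 6-1 and for the escalation clause in Section 6.6. In each case a rule followed as written can put a patient back on the dose that caused a DLT, and no other text clearly prevents it.

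The row conflict is confined to DLTs in the evaluation period and DLT-like toxicity in the first 21 days. Later on, the table applies without conflict. The number affected is likely to be small: about 1.5 of 25 if the 1/17 rate held and every such event qualified, with limits of 0.04 to 7.2 that mainly show how little is known. The documents give no usable rate for Grade 4 neutropenia beyond 72 hours.

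A reader might also infer that the MTD is compromised. It is not: under Section 6.6 the DLT is counted whatever dose follows. The matter should be fixed because the consequence is a safety one and the correction is short, not because the dose-finding result is in doubt.

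**What to change.** 1. In Section 6.5.3 and at the head of Table 6-1, state that any DLT in the DLT evaluation period, or DLT-like toxicity in the first 21 days, is managed under Sections 6.5.1 and 6.6 (discontinue, or reduce by at least 1 dose level), whatever the row says. Referring to the evaluation period also covers its extension to 28 days under Section 3.3.2.
2. If the sponsor wants Grade 3 infusion reactions handled case by case, name them as an explicit exception there and in Section 6.7.
3. In Section 6.6, after the reference to all patients, exclude those whose dose was reduced for toxicity.
4. While editing, state the resumption dose in the related Grade 4 non-hematologic row and align that row with Section 6.3.1.

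The cost is a few lines of text, with no added patients, visits or procedures. The downside is slightly lower exposure for the few patients affected. DLT counts and the MTD do not change.

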### **6.5.2 Criteria for Retreatment and Dose Delays**

TTI-621 is given as weekly infusions. Before each TTI-621 dose can be delivered, the patients' ANC must be  $\geq 1 \times 10^9/L$  and the platelet count must be  $\geq 75 \times 10^9/L$  or baseline. In addition, all other toxicity considered to be related to treatment with TTI-621 must have resolved to  $\leq$ Grade 1 or to the patient's baseline values with the exceptions listed below. If other AEs, not listed below, resolve to a level that is determined to be acceptable (and  $\leq$ Grade 2) for TTI-621, re-dosing is allowed based on a benefit-risk assessment by the investigator and medical monitor on a case by case basis. The decision will be documented.

Exceptions:

- Grade 2 gastrointestinal symptoms such as nausea, vomiting, and diarrhea that are easily treatable
- Grade 2 fatigue or other constitutional symptoms
- Grade 2 lymphopenia, neutropenia, and/or leukopenia in the absence of opportunistic infection
- Grade 2 thrombocytopenia in the absence of clinically meaningful bleeding
- Grade 2 anemia in the absence of shortness of breath and/or congestive heart failure
- Transient asymptomatic  $\leq$ Grade 3 laboratory abnormalities that is manageable with standard supportive care and considered not clinically significant following agreement between investigators and the sponsor or designees.

If the patient fails to meet the above-cited criteria for retreatment, initiation of the next dose of TTI-621 should be delayed for 1 week. At the end of that time, the patient should be re-evaluated to determine whether the criteria for retreatment have been met. If toxicity does not resolve by three weeks then the patient will be considered for removal from the study. If, in the opinion of the investigator and the medical monitor, it is in the patients' best interest to continue treatment with TTI-621 then the dose of TTI-621 should be reduced by at least 1 dose level after recovery of the toxicity or toxicities in question. In such circumstances, when a dose reduction of TTI-621 is required, no re-escalation of dose will be permitted.

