### 6.5.1 General Principles

Patients will be evaluated according to the Schedule of Assessments (See [Appendix D. Table 1](#) and [Appendix D. Table 2](#)) for possible toxicities that may have occurred after the previous dose(s). Toxicities are to be assessed according to the NCI CTCAE version 4.03. All toxicities that occur during the study will be actively managed following the standard of care per local institutional practice unless otherwise specified in the protocol. The investigator should try to the best of his/her ability to assess whether an AE is related or possibly related to study drug, and dosing actions of TTI-621 will then be considered accordingly.

In general, patients who have the TTI-621 dose held due to treatment-related or possibly related AE may resume study drug after resolution of the AE, at the same dose level or at a reduced level (dose reduction) by at least 1 dose level. When a dose reduction occurs, the TTI-621 dose will be reduced to the next lower dose either by following the ramp-up dosing regimen in Part 3 or on the established safe dose during phase 1b dose optimization part 4. If the initial dose adjustment does not provide sufficient relief, the dose of TTI-621 can be further reduced if the investigator considers that the patient is benefiting from study treatment and may benefit at a further dose reduced dose level of TTI-621. When a dose reduction of TTI-621 is required due to toxicity, no dose re-escalation will be permitted. If TTI-621 dosing is delayed for > 21 days for TTI-621-related or possibly related toxicities despite supportive treatment per standard clinical practice or more than 2 dose reductions are required in a patient, the investigator should consider discontinuing the patient from study treatment, unless the investigator, after risk-benefit assessment, considers that the patient may benefit from continued study treatment after resolution of AEs and when the re-treatment criteria are satisfied per [Section 6.5.2](#). The patient will continue to be followed for 30 days after the last administration of TTI-621.

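### Protocol 6.5.2 sets a platelet floor of 75 × 10⁹/L (or baseline) for every dose, then lists Grade 2 thrombocytopenia as an exception without saying which governs below the floor

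*Protocol*

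**What the plan says.** Four places in the protocol bear on whether a dose may follow a low platelet count.

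- **Section 6.5.2, count criterion.** "Before each TTI-621 dose can be delivered", the ANC must reach its own minimum and "the platelet count must be $\geq 75 \times 10^9/L$ or baseline".
- **Section 6.5.2, general toxicity criterion and exceptions.** The next sentence begins "In addition, all other toxicity considered to be related to treatment with TTI-621 must have resolved to" Grade 1 or lower, or the patient's baseline, subject to a list of exceptions. One item on that list is "Grade 2 thrombocytopenia in the absence of clinically meaningful bleeding". On failure, the section says: "If the patient fails to meet the above-cited criteria for retreatment, initiation of the next dose of TTI-621 should be delayed for 1 week".
- **Table 6-1.** All three thrombocytopenia rows use the 75 × 10⁹/L-or-baseline criterion for resuming treatment, and none carries a Grade 2 exception. The bleeding row also prints a grade boundary: "Grade 3 thrombocytopenia (platelet $<50 \times 10^9/L$ ) with clinical bleeding".
- **Section 9.5, Thrombocytopenia.** The summary of this risk says that delays or reductions are required when thrombocytopenia is Grade 3 or higher. It does not mention a hold for Grade 2.

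On grading, Section 6.5.1 states: "Toxicities are to be assessed according to the NCI CTCAE version 4.03". The grade limits themselves are not reproduced, apart from the boundaries printed beside individual criteria.

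**The concern.** The floor is a number and the exception is a grade, and within one section they appear to treat the same count differently. A site with a pre-dose count in the overlap could hold the dose, citing the floor, or give it, citing the exception. Each could point to text in 6.5.2.

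Section 9.5 classes thrombocytopenia as an important identified risk, so this rule should be read the same way everywhere. The ambiguity also travels. Section 6.5.1 refers to the 6.5.2 criteria for resuming after a DLT and for continuing after a delay of more than 21 days. Section 6.5.3 refers to 6.5.2 for the level of recovery that is acceptable. Section 6.6 makes dose increases in Part 4 depend on counts above the minimum required for dosing.

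On the analysis side, SAP 3.4 tabulates dose interruptions and their reasons. In Part 4, the reading applied decides which subjects have a delayed dose in the DLT period.

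**Working it through.** The plan gives no figure to reproduce. The check compares two sets of platelet counts, in units of 10⁹/L.

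**Inputs**
- Floor: 75, or the subject's baseline B (6.5.2).
- Exception: Grade 2 without clinically meaningful bleeding (6.5.2).
- Grade 3 or higher: below 50 (Table 6-1).
- Upper limit of Grade 2, U: not printed, so it is an assumption.
- Entry count: at least 75 in Part 4; at least 75 in Parts 2 and 3, or at least 50 with marrow involvement (4.1).

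**Step 1: lower edge of Grade 2.** Counts below 50 are Grade 3 or worse, so 50 is the lowest count that is not. The next milder grade is Grade 2, so Grade 2 starts at 50. No outside grading table is needed.

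**Step 2: the two sets.**
- A count c fails the floor if c < 75 and c < B.
- A count c matches the exception, absent bleeding, if 50 ≤ c < U.

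**Step 3: overlap.** Both hold when 50 ≤ c < min(U, 75, B). For a subject with B of 75 or more:

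| Assumed U | Overlap | Width |
|---|---|---|
| 60 | 50 to <60 | 60 − 50 = 10 |
| 75 or above | 50 to <75 | 75 − 50 = 25 |

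The overlap exists for any U above 50; U changes only its width. Example: with baseline 150, pre-dose count 50 and no bleeding, the floor calls for a 1-week delay while the exception lists the event as acceptable.

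**Step 4: does the baseline alternative remove it?** Only where the subject's own baseline is that low and the count has returned to it. Marrow involvement in Parts 2 and 3 allows this. Part 4 entry requires at least 75, and Section 7.2 says subjects should meet eligibility to proceed with the Day 1 infusion, so an eligible Part 4 subject has no such route.

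**Step 5: the two readings of 6.5.2.**
- *Exceptions apply to the retreatment criteria as a whole.* The exception then conflicts with the floor throughout the overlap.
- *Exceptions apply only to the sentence on other toxicity.* A count below both 75 and baseline is held under the floor whatever the exception says. A count below 75 that is back at baseline already satisfies the baseline alternatives in both sentences. The exception therefore changes nothing below 75. It could matter at 75 or above only if U exceeds 75, which the documents do not show.

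**Step 6: the other passages.** Table 6-1 sides with the floor, but its thrombocytopenia rows start from Grade 3 and 4 events. Section 9.5 does not match the floor, because a Grade 2 count below 75 and below baseline would be held under the floor and is absent from the 9.5 description.

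**The case against.** The strongest reply is that the criteria are cumulative. The count criterion stands alone; the next sentence adds a requirement for other toxicity, and the exceptions relax only that requirement. An exception to the second criterion cannot rescue a subject who fails the first, and failing the criteria means a delay. Table 6-1 supports this by naming the 75-or-baseline criterion three times with no Grade 2 qualification. On this view the bullet is surplus, not a contrary permission.

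Much of this stands. It is the better grammatical reading, so the stronger claim a reader might infer, that the protocol plainly both bars and allows the same count, is not established. What remains is that the list names thrombocytopenia expressly, that on this reading the item does nothing below 75, and that no sentence says which provision prevails. Table 6-1 does not expressly cover a subject whose worst event was Grade 2. Section 9.5 points the other way, although it is a risk summary and not an operating rule.

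Two further replies limit the reach. Sections 6.5.1 and 6.5.3 let the investigator and medical monitor agree on departures, which softens the ambiguity without removing it. The protocol also reports that platelets generally recovered before the next dose. In Section 1.8.4 the median pre-dose value before 0.5 mg/kg was 234, in 17 patients at Weeks 5–30; the other median, 257, was taken before the first dose and says little about retreatment. A median does not exclude counts of 50 to 75, and these data stop at 0.5 mg/kg while Table 3-4 plans up to 1.4 mg/kg.

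**Conclusion.** The point holds as an unresolved inconsistency in a dosing rule. For a subject with a higher baseline, counts from 50 up to the lower of 75 and the Grade 2 upper limit fail the floor yet match a listed exception. The exception either conflicts with the floor or is inoperative below 75, and the protocol does not say which. This rests on the Grade 3 boundary printed in Table 6-1; only the width of the band depends on the unprinted upper limit.

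The number of subjects affected cannot be derived from the documents and may be small. The direct analytic effect is on the dose-interruption tabulations and on which Part 4 subjects have a delayed dose in the DLT period.

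A reader might go further and infer that this wording itself costs subjects their DLT evaluability. The documents do not support that. Protocol 3.3.2 allows the period to extend to 28 days when a non-DLT event requires a hold under Section 6.5, whereas SAP Section 2 treats a delay of more than 3 days for reasons other than DLT as unevaluable. Any loss would come from that mismatch, which is a separate issue. The present wording affects only who is held. The correction is worth making because it is cheap and concerns an important identified risk.

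**What to change.** Reconcile four texts so that one rule governs: the platelet floor in 6.5.2, the Grade 2 thrombocytopenia exception in 6.5.2, the re-treatment criterion in Table 6-1, and the Section 9.5 description of when delays or reductions are required. Section 6.5.2 should state whether the exceptions can override the count criteria. Which rule applies is for the sponsor and its clinical advisers; no threshold is proposed here.

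For subjects already treated, record which reading was applied when a pre-dose count fell in the overlap, so that the interruption tables can be interpreted. The cost is a wording amendment and, for past data, a short check of pre-dose counts against dosing records. Sample size and analysis methods are unaffected.
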